Power analysis. To determine the sample size, we conducted an a priori power analysis with the software program G*Power. We conducted the power analysis to make sure we would be able to detect differential effects on key mechanisms of change and community stability between participants allocated into the two study conditions. We powered the study based on conducting multivariate analysis using ANCOVA. We used a small effect size estimate - Cohen's d of .15 - based on guidance and data from the Clinician Administered PTSD Scale on a similar population.⁶⁷ Being able to detect small effects is important as we may find minimal difference between group members. Using an alpha of .05 and powered at a .80 level across two groups with up to seven covariates, a sample of 352 would allow us to detect small effects. Thus, a targeted sample size of 400 provides statistical power greater than .80, giving us strong confidence that we will be able to detect even small difference between study conditions.

Recidivism. Survival analysis will be conducted to analyze time-to-event on recidivism outcomes (i.e., time to arrest and time to incarceration). Participants without the occurrence of the events will be censored at their last known event-free time point. Survival curves will be constructed using Kaplan-Meier estimates. Using the Kaplan-Meier curve allows us to derive the median, or that time at which 50% of cases of the event of interest has occurred, and the mean (i.e. the average time it took for the event to occur). Although there are several methods available to analyze time-to-event curves, the proposed study uses a Cox proportional hazard model which is a regression method for survival data and has been used in previous criminal justice-related studies. The Cox model allows for the identification of differences in survival rate due to study condition and prognostic factors, such as covariates. Further, the Cox model provides an estimate of the hazard ratio and its confidence interval. There are two underlying assumptions of the Cox proportional hazard model: (1) the hazard ratios of two people are independent of time and (2)

are valid only for time independent covariates. For the current study, results will be displayed for comparison of survival distributions for three years post-release.

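### The ANCOVA sample size of 352 fits Cohen's f = .15 (d = .30), not the stated d = .15; at d = .15 the power with 400 participants is about .32, not above .80

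*SAP*

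**What the plan says.** The SAP's first power analysis, which covers key mechanisms of change and community stability, states its inputs in a few sentences. The software is G*Power and the model is ANCOVA: "We powered the study based on conducting multivariate analysis using ANCOVA". The effect is given as follows: "We used a small effect size estimate - Cohen's d of .15". It is attributed to guidance and to PTSD-scale data from a cited study in a similar population. The remaining inputs and the result are "Using an alpha of .05 and powered at a .80 level across two groups with up to seven covariates" and "a sample of 352 would allow us to detect small effects". The SAP then says that "a targeted sample size of 400 provides statistical power greater than .80", and expresses strong confidence that even small differences between conditions will be found.

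Protocol section 5.0 gives 1:1 allocation, and the SAP's recidivism power analysis gives 200 per arm. Neither document states a proportion of outcome variance explained by covariates, a baseline-to-follow-up correlation, the sidedness of the test, or a dropout allowance for this calculation.

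**The concern.** A standardised difference of .15 is very small, and about 350 participants is far too few to detect it with 80% power in a two-arm comparison. The stated size looks like the answer for an effect twice as large. ANCOVA power is commonly parameterised by Cohen's f. For two equal groups f is half of d, so the same .15 means different things on the two scales.

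The Protocol's Study Summary makes improvement in the mechanisms of change the primary objective, and this is the power statement behind it. The SAP itself says that being able to detect small effects matters because the groups may differ little. If the true effect is d = .15, and covariates add no precision, the trial would miss it about two times in three. A reader relying on the SAP could then take a null result as evidence against an effect of that size.

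**Working it through.** **Inputs.** From the SAP power analysis: two groups, up to seven covariates, alpha .05, target power .80, effect .15 labelled d, stated N = 352, planned N = 400. From Protocol section 5.0: 1:1 allocation. Assumed, because not stated: a two-sided test (which the 1-df ANCOVA F test is), everyone analysed, and no precision gain from covariates. The last assumption is relaxed in step 4.

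**Method.** Noncentral F test with df1 = 1, df2 = N − 2 − 7 and noncentrality λ = N·f². Power is the probability that this F exceeds the central F critical value at alpha .05. For two equal groups, f = d/2.

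**1. Reproducing the plan's figure, reading .15 as f (d = .30).**
- N = 351: λ = 351 × .0225 = 7.90, power .800. This is the smallest N that reaches .80.
- N = 352 (two arms of 176): λ = 7.92, df2 = 343, power .801.
- N = 400: λ = 9.00, df2 = 391, power .849.

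Both of the SAP's figures follow. The number of covariates hardly matters: N is 351 with 0, 1 or 7.

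**2. The effect as stated, d = .15, so f = .075.**
- N = 352: λ = 352 × .005625 = 1.98, power .289.
- N = 400: λ = 2.25, power .322.
- N needed for .80: 1,398 (λ = 7.86). A normal approximation for two means gives 698 per arm, or 1,396.

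The ratio 1,398/351 is about 4, as expected when the effect is halved.

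**3. Other readings of the inputs.**
- One-sided test at d = .15: N = 1,101; power .41 at 352 and .44 at 400.
- .15 read as f²: N = 55.

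Neither gives 352.

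**4. Precision gained from covariates.** If d = .15 is a raw effect and covariates explain a share R² of outcome variance, the adjusted effect is f = .075/√(1 − R²). The R² values below are assumptions.

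| R² | Power at N = 400 |
|---|---|
| 0 | .32 |
| .10 | .35 |
| .25 | .41 |
| .40 | .49 |
| .50 | .56 |
| .70 | .78 |

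Power of .80 needs R² of about .715 at N = 400, or .75 at N = 352. At R² = .75, √(1 − R²) = .5, so a raw d of .15 becomes an adjusted d of .30.

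**5. What the trial can detect.** The smallest d with 80% power is .28 with 400 analysed and .30 with 352.

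**6. Loss to follow-up.** Having 352 analysed means retaining 352/400 = 88%. The documents give no expected retention. As illustrations, 80% (N = 320) gives power .76 and 70% (N = 280) gives .71, both at d = .30.

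**The case against.** The strongest counter-argument is that .32 is one scenario. It assumes either that d is already on the covariate-adjusted scale or that the covariates explain nothing. The planned analysis has up to seven covariates, and a useful set could raise power to .41 or even .56. That is fair, and .32 should carry its conditions. It does not rescue the SAP. No R² is stated, the covariates it names as examples are race, other program participation and criminal history, and .80 would need R² above .7.

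Second, the G*Power entry is not shown, so it is an inference that .15 was entered as f. This stands. The numerical match makes it the likeliest explanation, but the defect does not depend on it, because 352 does not follow from d = .15 whatever the cause.

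Third, relabelling the effect as f = .15 may be the wrong repair if the cited data support d = .15. This also stands and shapes the fix below.

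Fourth, the 48 participants above 352 are a margin in practice, and the plan includes tracking, interview payments and possible multiple imputation. These are sensible measures, but the SAP does not present the margin as an attrition allowance, and none of them enters the calculation.

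**Conclusion.** The concern holds. The stated effect and the stated sample size are incompatible by a factor of two in effect size and about four in N. At d = .15, power with all 400 analysed is about .32 for a two-sided test with no covariate gain, and it stays below .80 unless covariates explain roughly 70% or more of outcome variance. The design is adequate for d = .30, with power .85 at 400, but that is not what the SAP says it was planned to detect. Attrition would lower every one of these figures. The separate recidivism power analysis is not affected. Because this is the power statement for the primary objective and the error is in the favourable direction, it must be corrected.

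**What to change.** 1. Check the cited PTSD-scale data and the G*Power entry to establish which effect was intended.
2. If it was f = .15, replace the label with Cohen's f of .15 (d = .30) and confirm that the cited data support d = .30. State that 400 analysed gives power .85 for d = .30 and .32 for d = .15.
3. If d = .15 really is the planning effect, state that power at 400 is about .32 without covariate gain. Any higher figure needs a stated and justified R².
4. In either case, give the smallest detectable effect (d = .28 with 400 analysed) and remove the claim about detecting even small differences.
5. Report the same quantities for the number expected to complete the follow-up interviews, with the assumed retention stated.

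The cost is a short revision of the SAP text and a less favourable power statement. Enrolment, data collection and the planned test do not change.

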5.3 Research team members have experience working with people with trauma histories. This is important so they can successfully assess if there are adverse behaviors or thoughts during service delivery (treatment group) and during data collection interviews (all participants). All interviews are conducted one-on-one so the research team member can assess for adverse reaction to the data collection or treatment delivery.

6.4 Data will be collected from participants during one-on-one interviews. Interviews will occur in a private space, where the conversation between the team member and individual cannot be

heard. Data will be recorded in RedCap computer software. Potential participants will complete 12 -count trauma checklist as a screener for assessing for presence of at least one LTE. Eligible participants will plan to release to one of our four Florida counties. Participants will be consented using a Florida State University IRB consent form. If the individual meets screening criteria and consents into the study, the research team member will complete the baseline interview.

All consented participants (treatment and control) will complete a series of interviews. Baseline interviews will occur immediately after consent and occur in prisons. Follow-up interviews will be conducted in the community and timepoints include (1) after the conclusion of the program period, (2) three months after the conclusion of the program period, and (3) nine months after the conclusion of the program period.

6.5 Measures were selected based on the quality of established psychometric evidence and use with criminal justice-involved or other at-risk populations.

- Risk Assessment. Spectrum is the assessment tool used by FDC that identifies risk factors for criminal behavior. Scores on Spectrum range 1-5. The assessment is given to individuals at intake, periodically throughout incarceration and then again under a year before they release and measures an individual's risk to recidivate.
- Trauma screener. A dichotomous Yes/No measure of 12 LTEs from the Trauma Assessment for Adults serves as the trauma screening tool. Participants are identified as eligible if they have experienced at least one LTE.
- Demographics. Age, race/ethnicity, marital status, level of education at release, age at first offense, number of prior incarcerations, most serious offense, and current sentence length will be collected from FDC administrative databases.

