Power Analysis. The Bureau of Justice Statistics (BJS) 2005-2014 data show that 76.5% of prisoners age 24 or younger released in 2005 were arrested within three years of release. Specifically, 51.8% were arrested within the first year, an additional 17% in the second year, and an additional 7.7% in the third year. Our goal is to reduce recidivism by 28% over three years. Using these data and the method described by Collett (2003, pp. 299-312), we calculate that the hazard ratio of recidivism for this study at 1.39, meaning that members of the control group will recidivate 39% faster than participants receiving the targeted treatment. Using the same BJS data, we calculated the median survival time (pre-recidivism) for members of the control group at 17.28 months. The median survival time suggests that 50% of the control group will recidivate by 17.28 months after release from incarceration. These data provided the basis for the power calculation. The power analysis was conducted using PS software.⁷⁸ Results show that for a study with 200 experimental participants and 200 control participants, a hazard ratio of recidivism of 1.39, and a median survival time for the control group of 17.28 months, we will be able to reject the null hypothesis that the treated and control survival curves are equal with a probability (power) of .810. The Type I error probability associated with this test of this null hypothesis is 0.05. Therefore, the study will have adequate statistical power.

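### The SAP claims power above .80 at the 400 men recruited and states no attrition assumption: if .15 is Cohen's f the margin covers about 12% loss, and if it is Cohen's d power is .32 before any loss

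*SAP*

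**What the plan says.** The power paragraph for Key Mechanisms of Change and Community Stability in the SAP gives these inputs: "We powered the study based on conducting multivariate analysis using ANCOVA"; "We used a small effect size estimate - Cohen's d of .15"; and "Using an alpha of .05 and powered at a .80 level across two groups with up to seven covariates". It reports that "a sample of 352 would allow us to detect small effects" and then concludes: "Thus, a targeted sample size of 400 provides statistical power greater than .80". The same sentence goes on to express strong confidence that even small differences will be found.

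The 400 is the number to be recruited (Protocol, Study Summary and sections 8.0 and 11.0). The outcomes concerned are measured mainly by interview. Baseline takes place in prison. After that, "Follow-up interviews will be conducted in the community" (Protocol section 5.0, item 6.4): at the end of the program period, and three and nine months later. Section 13.0 foresees removal of participants for several reasons, one being release from prison after recruitment has ended, but puts no number on it.

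On missing data, the SAP's Analytic Plan mentions participant tracking, incentives and multiple imputation as an option. No loss rate, expected number analysed or inflation for dropout appears in either document.

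**The concern.** Power depends on the men who supply an outcome, not on the men enrolled. The SAP states its power at the enrolment target and presents the surplus over 352 as additional power rather than as a reserve for loss. Complete follow-up is a demanding condition here. Participation can last up to 18 months, all three follow-up interviews fall after release, and neither document describes interviewing men who are back in custody.

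Mechanisms of change are the primary objective. If fewer men are analysed than the statement supposes, a null result could be read as evidence against a small effect that the trial had limited power to detect. The label on the effect size adds to this, because whether the stated power is right even at 400 depends on what .15 means.

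**Working it through.** **Inputs.** From the SAP: alpha .05, target power .80, two groups, seven covariates, effect size .15, required N 352, target N 400. From the Protocol: 1:1 allocation. Loss rates are not given; 10% to 40% is my assumption, with equal loss in both arms and analysis of men with an observed outcome.

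**Formula.** ANCOVA F-test for one two-level factor: df1 = 1, df2 = N − 2 − 7 = N − 9, noncentrality λ = N·f². Power is the probability that a noncentral F exceeds the 5% critical value of the central F. For two equal groups f = d/2.

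**Step 1. Reproduce the 352.**
- With f = .15 (d = .30): at N = 352, λ = 352 × .0225 = 7.92, df2 = 343, power .801. At N = 350 power is .799. The smallest N is 351, or 352 with equal arms. The stated figure reproduces.
- With d = .15 (f = .075): at N = 352, λ = 352 × .005625 = 1.98, power .289. The N needed for .80 is 1,398 (1,396 by normal approximation; 1,100 if one-sided). The stated figure does not reproduce.

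**Step 2. The margin.** 400 − 352 = 48, and 48/400 = 12%.

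**Step 3. Power by number analysed.** The last column is the standardised difference, in covariate-adjusted standard deviations, that has power .80 at that N. It does not depend on how .15 is read.

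| Assumed loss | Analysed | Power, f = .15 | Power, d = .15 | Detectable difference at .80 |
|---|---|---|---|---|
| 0% | 400 | .849 | .322 | .28 |
| 10% | 360 | .810 | .295 | .30 |
| 12% | 352 | .801 | .289 | .30 |
| 20% | 320 | .763 | .267 | .31 |
| 30% | 280 | .706 | .240 | .34 |
| 40% | 240 | .638 | .212 | .36 |

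**Step 4. Could covariates rescue d = .15?** If .15 is an unadjusted difference, adjustment raises it to .15/√(1 − R²). Reaching .30 needs R = √(1 − (.15/.30)²) = .87. A multiple correlation that high with the outcome is not plausible.

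**The case against.** The quoted sentence is true on the reading that reproduces 352: power at 400 is .85. The 48 extra men work as a cushion whatever they are called, and at 10% loss power is still .81. It would therefore be wrong to infer that the design leaves no room for loss. The fair criticism is that the room is neither labelled nor justified.

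Nothing in the documents shows that loss will exceed 12%. The plan has tracking, a payment of $30 for each post-release interview (Protocol 12.2) and a mobile team (20.1). No single primary time point is named, and loss at program end may differ from loss at nine months. The 20% to 40% range is an assumption, and that the trial will fall below .80 through attrition is not established.

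A reader might also infer from the SAP's recidivism section ("51.8% were arrested within the first year") that half the men will be arrested in year one and so miss interviews. The documents do not support this. That figure is national and covers releases aged 24 or younger, while the trial enrols ages 18 to 35. The SAP's own control median is 17.28 months; under a constant hazard (my assumption) that gives 1 − 0.5^(12/17.28) = 38% of controls by 12 months. Arrest is also not the same as a missed interview, and the Protocol does not say that an arrested man goes uninterviewed.

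Multiple imputation is a partial answer at best: it is optional, and it generally recovers little power when the outcome itself is missing.

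What stands is that a power figure for the primary objective is given at the number recruited, with no stated assumption about the number analysed.

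**Conclusion.** The point holds as an omission, not as an arithmetic error. On the f = .15 reading, the claim of power above .80 survives loss of about 12% and fails beyond it, reaching .76, .71 and .64 at assumed losses of 20%, 30% and 40%. On the d = .15 reading, which is what the text says, it fails with no loss at all. It would be wrong to say that attrition takes power below .80 on the SAP's own input, because the written input is d and needs no attrition to fall short. The conflict between d and f is the larger defect, and a table of power by retention cannot be completed until it is settled. The recidivism analyses draw on corrections and law-enforcement databases and fall outside this point.

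**What to change.** In the SAP's first power paragraph:

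1. State whether .15 is Cohen's d or Cohen's f, and correct the label or the sample-size figure so that the two agree.
2. Replace the sentence on 400 men with power at the number expected to be analysed, for example at 90%, 80%, 70% and 60% retention, and label the retention rates as assumptions.
3. Give the smallest standardised difference detectable with .80 power at each number: about .28 at 400, .30 at 360, .31 at 320, .34 at 280 and .36 at 240.
4. Delete the clause expressing strong confidence.

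This changes SAP wording only; enrolment, design and conduct stay as they are. The cost is a stated power that reads less favourably.
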